### *Metabolic and Respiratory Quotient Testing*

An indirect calorimetry device (Parvo Medics TrueOne 2400) was used to measure RMR and RQ. The device was calibrated according to the manufacturer's instructions. Participants were instructed to lay completely still and relax for 15 minutes. The first 5 minutes was allotted for acclimatization. The Parvo Metabolic Cart measures the volume of oxygen consumed ( $VO_2$ ) and the volume of carbon dioxide produced ( $VCO_2$ ) by the patient on a breath-by-breath basis. The ratio of these gases is used to determine the Respiratory Quotient (RQ), providing information regarding substrate utilization. The parameters that were measured and used for analysis were RMR,  $O_2$  volume ( $VO_2$ ),  $CO_2$  volume ( $VCO_2$ ), the RQ, percentage of utilized fat (Fat%), and percentage of utilized carbohydrates (CHO%).

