## **Study Protocol**

### *Study Design*

This study followed a randomized, double-blinded, crossover design. Participants reported to the clinical site on two separate visits. Participants were instructed to abstain from exercise on testing day and arrive at the lab fasted (no food or caffeine ingestion for 4 hours prior). Testing sessions consisted of two visits per week with a minimum of 24 hours between visits. During the first visit demographics and anthropometrics were assessed. At every testing each subject completed the following protocol: baseline Metabolic Rate and Respiratory Quotient. Immediately after baseline test, participants consumed supplement 1 or 2. Metabolic Rate and Respiratory Quotient Testing was repeated at 60, 120, and 180 minutes after supplementation. All participants underwent an informed consent process in accordance with the Declaration of Helsinki and an approved IRB protocol approved by institutional review board at Nova Southeastern University, IRB number 2024-209.

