## **Statistical Analysis**

All data is expressed as mean SD. Basic descriptive statistics were used for participant demographics and anthropometrics. A paired t-test was used to assess any differences between the 100 and 200 mg doses for REE and RER at baseline. To determine the effects of Gyngerlean™ on energy expenditure, a repeated-measures analysis of variance (ANOVA) was used to determine differences between 100mg and 200mg doses for the 60, 120- and 180-time intervals. A repeated Dunnett's multiple

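### Does listing six overlapping gas-exchange parameters, with none called primary, inflate the chance of a false dose effect?

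*Combined protocol and SAP*

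**What the plan says.** Three places in the combined protocol and SAP bear on which outcomes are analysed.

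- **Metabolic and Respiratory Quotient Testing:** "The parameters that were measured and used for analysis were RMR", followed by VO2, VCO2 and then "the RQ, percentage of utilized fat (Fat%), and percentage of utilized carbohydrates (CHO"%). That makes six. On their overlap the section says: "The ratio of these gases is used to determine the Respiratory Quotient (RQ), providing information regarding substrate utilization".
- **Study Design:** "Metabolic Rate and Respiratory Quotient Testing was repeated at 60, 120, and 180 minutes after supplementation". Only two outcomes are named here.
- **Statistical Analysis:** the baseline paired t-tests cover REE and RER (taken here as RMR and RQ). The only efficacy test that can be read has one target: "To determine the effects of Gyngerlean™ on energy expenditure, a repeated-measures analysis of variance (ANOVA) was used". It addresses "differences between 100mg and 200mg doses for the 60, 120- and 180-time intervals".

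No outcome is labelled primary and no significance level appears before the section breaks off, mid-sentence, as it introduces a Dunnett procedure.

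**The concern.** Read side by side, the sections point to six outcomes, two, or one. A reader cannot be sure how many receive the comparison of doses, or which one carries the conclusion.

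Two things could go wrong. First, if all six are tested at the same level and any significant result is reported as a dose effect, the error rate rises above that of one test. A null result on energy expenditure could be replaced by a positive one from elsewhere in the list. Second, the parameters are not separate pieces of evidence. Under the usual conversions a chance shift in RQ also appears in Fat% and CHO%, and could be presented as three findings that agree. A Dunnett procedure compares levels within one outcome, so it would not by itself deal with either problem.

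**Working it through.** The readable text gives no sample size, significance level or error rate, so there is no figure of the plan's own to reproduce. The check asks how large the rise would be if all six were tested.

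**Inputs from the document:** the six parameters; RQ = VCO2/VO2; a two-visit crossover; two doses; post-dose times of 60, 120 and 180 minutes.

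**Assumed inputs:** two-sided 5%; n from 10 to 40; mean VO2 250 mL/min with a between-person SD of 15%; mean RQ 0.82 (SD 0.04); within-person error of 5-7% on each gas; correlation between the two gas errors from 0 to 0.98; and the usual conversions

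- RMR proportional to 3.941 × VO2 + 1.106 × VCO2
- Fat% = 100 × (1 - RQ)/0.3
- CHO% = 100 - Fat%

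**Step 1: how many distinct tests are there?** A dose difference in Fat% is -(100/0.3) = -333 times the difference in RQ, and the CHO% difference is the same with the sign reversed. A paired t statistic does not change in size when the data are rescaled, so RQ, Fat% and CHO% give one and the same test. RMR is mostly VO2: at RQ 0.82 the VO2 share is 3.941/(3.941 + 1.106 × 0.82) = 3.941/4.848 = 81%. The six parameters therefore carry about two independent quantities.

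**Step 2: reference values.**

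- Six independent tests: 1 - 0.95^6 = 26.5%. This does not apply, because the outcomes overlap.
- Two independent tests: 1 - 0.95^2 = 9.75%.
- Large-sample ceiling for any number of linear combinations of two normal quantities: P(chi-square on 2 df > 1.96^2) = exp(-3.84/2) = 14.7%.

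**Step 3: simulation with no dose effect.** With two doses, the dose main effect of the repeated-measures ANOVA equals a paired t-test on each person's post-dose mean (F = t squared). The table gives the chance of at least one false dose effect.

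| Setting | RMR only | RMR and RQ | All six |
|---|---|---|---|
| 5% error on both gases, n = 12, 20, 30, correlation 0-0.95: range | 4-6% | 8-11% | 10-13% |
| Same settings: median | 4.9% | 9.4% | 12.3% |
| Wider inputs, correlation 0-0.9 | about 5% | - | 10.2-13.4% |
| Correlation 0.95-0.98, equal errors | about 5% | - | 10.3-11.4% |
| Correlation 0.95-0.98, unequal errors (5% and 7%) | about 5% | - | 7.6-9.6% |

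A separate simulation of the full dose-by-time ANOVA gave 11.2-13.2% for the dose main effect over all six outcomes.

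**Step 4: where does the rise come from?** On the medians, adding RQ to RMR costs 9.4 - 4.9 = 4.5 points. The other four parameters add 12.3 - 9.4 = 2.9. So 4.5 of the 7.4 points, or 61%, come from having two named outcomes rather than from the length of the list. The multiple is about two but not always: in the last row it falls to 7.6/5 = 1.5.

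**Step 5: what does the text commit to?** The dose ANOVA is stated for energy expenditure, and no dose test is stated for VO2, VCO2, RQ, Fat% or CHO%. The same section says data are summarised by means and SDs, so being used for analysis can mean descriptive reporting, or serving as inputs to RMR and RQ. Followed literally, the plan sits in the RMR-only column.

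**The case for a change.** The strongest case for a change is that the mismatch between one, two and six outcomes is visible without the lost text, and that the phrase about parameters used for analysis makes six dose tests a plausible reading. A few sentences would settle it at no cost in data. The error rate could also exceed the headline. If a significant dose-by-time interaction also counts as a dose effect, the simulation gives about 9-10% for RMR alone and 21-25% for all six. If the three times were tested separately without adjustment, the figures are 9-15% and 21-34%.

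Part of this stands. The sections could be better aligned, and RQ, Fat% and CHO% should not be read as independent support. The rest does not carry through. The higher figures also rise for RMR alone, so much of the increase reflects how time is handled rather than the number of outcomes, and the separate-times figures depend on a Dunnett step that cannot be read. An outcome order may stand in the same lost text, and its absence from a cut-off section cannot be counted against the plan. The natural clarification, RMR primary by the planned ANOVA, is what the Statistical Analysis section already aims at. If the data had been seen, a ranking added now would have to be labelled post hoc and would not bring the rate back to 5%.

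**Conclusion.** No change to the plan follows. This is a gap in labelling that an analyst fills sensibly by taking the one efficacy test that is described, the dose comparison "on energy expenditure, a repeated-measures analysis of variance (ANOVA) was used to determine differences between 100mg and 200mg doses", as the test that carries the conclusion. On that reading the false-positive chance for the dose main effect is about 5%.

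The doubling to roughly 9-13% (7.6% at the lowest simulated setting) arises only if all six parameters are tested for dose and any significant result is claimed, which the readable text does not say. Most of that rise would come from adding RQ to RMR. The figures rest on an assumed two-sided 5%, assumed sample sizes and error structures, and the usual conversions from the two gas volumes. If the complete section showed that all six outcomes were tested and claimed on an equal footing, the point would need to be looked at again.

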## **Statistical Analysis**

All data is expressed as mean SD. Basic descriptive statistics were used for participant demographics and anthropometrics. A paired t-test was used to assess any differences between the 100 and 200 mg doses for REE and RER at baseline. To determine the effects of Gyngerlean™ on energy expenditure, a repeated-measures analysis of variance (ANOVA) was used to determine differences between 100mg and 200mg doses for the 60, 120- and 180-time intervals. A repeated Dunnett's multiple

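### Does presenting all data as mean and SD leave the crossover's dose comparison without a usable measure of precision?

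*Combined protocol and SAP*

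**What the plan says.** The design is stated in Study Design: "This study followed a randomized, double-blinded, crossover design". Each participant attends twice and is measured at baseline and at 60, 120 and 180 minutes after the supplement.

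Statistical Analysis opens with the presentation rule, "All data is expressed as mean SD" (a plus/minus sign was probably lost when the PDF was read). It then names three inferential steps:

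- At baseline: "A paired t-test was used to assess any differences between the 100 and 200 mg doses for REE and RER at baseline".
- After dosing: "a repeated-measures analysis of variance (ANOVA) was used", and this "was used to determine differences between 100mg and 200mg doses for the 60, 120- and 180-time intervals".
- A multiple-comparison step, of which only "A repeated Dunnett's multiple" can be read before the text breaks off.

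The readable text mentions no confidence interval, standard error, SD of paired differences, sample size or power. It does not say whether the means and SDs are of raw readings or of changes from baseline.

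**The concern.** A crossover gains its efficiency by removing differences between people from the treatment comparison. The SD of readings at one dose puts those differences back. For resting metabolic rate and gas volumes, where body size plausibly matters, it may be much larger than the variability that decides the dose comparison. Two means and two SDs do not show how closely a person's two visits agree, and the standard error of the paired difference depends on that agreement.

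The wording of the rule is universal, and demographics have their own sentence straight after it, so it can be read as covering the outcome results too. On that reading, a trial of two active doses with no stated sample size or detectable difference would report its main result as two summaries and a test. A null result could then reflect either true similarity or too little information, and a reader might not know which. A genuine within-person difference could also look small beside the displayed spread.

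**Working it through.** The readable text states no sample size, power, SD or correlation, so there is no figure of the plan's own to reproduce. What follows is illustration under assumed inputs.

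**Inputs.** From the documents: two doses compared within person. Assumed: the same SD at both doses, set to 1; within-person correlation ρ of 0.5 to 0.95; n = 20 with complete data.

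**Step 1: displayed SD against SD of the paired difference.** SD(diff) = SD × √(2(1 − ρ)), so the ratio SD / SD(diff) is 1 / √(2(1 − ρ)).

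| ρ | SD(diff) | SD / SD(diff) |
|---|---|---|
| 0.5 | √1.0 = 1.000 | 1.0 |
| 0.8 | √0.4 = 0.632 | 1.6 |
| 0.9 | √0.2 = 0.447 | 2.2 |
| 0.95 | √0.1 = 0.316 | 3.2 |

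The mismatch depends on ρ. It is absent at 0.5, and below 0.5 the displayed SD is the smaller of the two. High ρ is plausible for metabolic rate. It is less obvious for respiratory quotient and the fat and carbohydrate percentages, which are a ratio and percentages in which body size largely cancels.

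**Step 2: do the summaries fix the precision?** Take displayed results of 0.0 (SD 1.0) and 0.2 (SD 1.0). The 95% half-width is t(0.975, 19) × SD(diff) / √20 = 2.093 × SD(diff) / 4.472 = 0.468 × SD(diff).

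| ρ | Difference | Half-width | 95% CI | p |
|---|---|---|---|---|
| 0.5 | 0.20 | 0.468 | −0.27 to 0.67 | 0.38 |
| 0.9 | 0.20 | 0.209 | −0.01 to 0.41 | 0.06 |
| 0.95 | 0.20 | 0.148 | 0.05 to 0.35 | 0.01 |

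The same display fits all three rows, so the per-dose SDs alone do not give the precision. The point estimate is the same in every row, because with complete pairs the mean of the differences equals the difference of the means.

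**Step 3: what a within-person test adds.** For a single paired contrast, the difference, n and an exact p-value return the interval. In the middle row, t = 0.20 / (0.447 / 4.472) = 0.20 / 0.100 = 2.0, which is what p = 0.060 on 19 degrees of freedom implies. Working back, SE = 0.20 / 2.0 = 0.100 and the half-width is 2.093 × 0.100 = 0.209, as tabulated. This route works poorly if p is rounded or given only as a threshold, or if the difference is near zero. It does not apply to a test with several degrees of freedom, such as a dose-by-time interaction.

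**Step 4: what the text commits to.** The rule says how data are expressed. It does not say that the dose comparison will be summarised only in that way. The comparison has its own sentences, and the methods they name are within-person methods. Those sentences cannot be read to the end.

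**The case for a change.** The strongest case for a change is that a p-value is neither an effect size nor a statement of precision. The only reporting rule that can be read supplies neither for the paired difference, and the remedy is one sentence with no new data. The gap would recur over six measured parameters and three post-dose times. With both compared supplements active and no detectable difference stated, a null dose comparison is a realistic result, and an interval is the natural way to interpret it.

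Much of this stands. An interval is better reporting, per-dose SDs do not replace one, and the back-calculation from p is fragile in exactly the null case that matters most.

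It does not stand as a fault in the plan. The dose difference itself is not lost, since it can be read from the two means. The documents give no variance components, so dominance of between-person spread is an assumption, and it is weaker for the ratio and percentage outcomes. No figure or bar display is described, so a prediction of overlapping bars goes beyond the text. Silence about intervals, in a section whose last readable sentence is unfinished, is not evidence that none was planned.

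**Conclusion.** No change to the plan is called for. Mean and SD is a valid description of the readings at each dose and time, and it does not prevent an estimate with an interval from being reported beside it. Followed as written, the visible plan gives correct descriptive summaries and tests that respect the pairing. Specifying an interval would add an item to the report and leave every test, estimate, error rate and measurement as it is.

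The size of the mismatch is conditional: the displayed SD is 1.0 to 3.2 times the SD of the paired difference for ρ from 0.5 to 0.95, assuming equal SDs. The illustrative intervals also assume n = 20 and complete pairs. None of these inputs comes from the documents.

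An analyst writing up this crossover would sensibly give the mean 200 minus 100 mg difference with its 95% interval at each time, and would judge any claim of no difference from that interval. The present wording already allows this. The conclusion is limited to the readable text; whatever follows the start of the multiple-comparison sentence could not be assessed.

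### Baselines are compared only by dose and the ANOVA names no visit or order term, so a shift between the two crossover visits would go unseen and unadjusted

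*Combined protocol and SAP*

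**What the plan says.** Study Design states: "This study followed a randomized, double-blinded, crossover design", and "Participants reported to the clinical site on two separate visits". On spacing it says: "Testing sessions consisted of two visits per week with a minimum of 24 hours between visits". A baseline reading opens each visit, and then: "Immediately after baseline test, participants consumed supplement 1 or 2". The visit-2 baseline is therefore always taken after the visit-1 supplement. Statistical Analysis names only 100 mg and 200 mg of one product. Read together, the two sections describe two active visits, with no placebo visit in the visible text.

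The only baseline analysis shown is this: "A paired t-test was used to assess any differences between the 100 and 200 mg doses for REE and RER at baseline". For the main comparison, "a repeated-measures analysis of variance (ANOVA) was used"; it was "used to determine differences between 100mg and 200mg doses for the 60, 120- and 180-time intervals". That sentence is complete and names neither visit nor dose order. The next one stops at "A repeated Dunnett's multiple", so the reference level for Dunnett's test, and anything after it, cannot be read. The visible text gives no sample size, SD, order ratio or reason for the 24-hour minimum.

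**The concern.** Residual effect of the first dose, habituation to lying still under the calorimeter, or any other difference between the first and second session would show as a shift from the visit-1 to the visit-2 baseline. A by-dose comparison mixes the two visits within each dose and so averages that shift away. A reader who sees a non-significant baseline test may conclude that both visits began from the same state, which the test cannot establish.

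Three things are at stake:

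- the precision of the dose comparison, because an unmodelled visit shift goes into the error term;
- its bias, if the two orders are unequally filled or carryover differs by dose;
- the meaning of any change from the visit-2 baseline. Without a placebo visit, a statement about the product's own effect on energy expenditure would have to lean on such a change.

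**Working it through.** **Inputs.** From the documents: two visits, at least 24 hours apart; a pre-dose baseline at each; 100 versus 200 mg; a paired t-test by dose; an ANOVA with no stated visit or order term. There is no figure in the plan to reproduce. Assumed here: 20 participants, 10 per order (12:8 as an alternative), SD of the within-person difference between visits = 1, two-sided 5% level.

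**Step 1: what the by-dose baseline test estimates.** Let p be the share given 100 mg first, π the period shift, and L100 and L200 the residual effect of each first dose on the visit-2 baseline.

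- 100 then 200: baseline(200) − baseline(100) = π + L100
- 200 then 100: baseline(200) − baseline(100) = −(π + L200)
- Mean = p(π + L100) − (1 − p)(π + L200)

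At p = 0.5 this is (L100 − L200)/2. The period shift and any shared carryover drop out, whatever their size.

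**Step 2: rejection rates at baseline (simulated, 10:10).** The by-visit test is the visit-2 minus visit-1 difference, stratified by order.

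| L100, L200 (SD) | By-dose t-test | By-visit test |
|---|---|---|
| 0, 0 | 5% | 5% |
| 0.5, 0.5 | 3% | 56% |
| 0.8, 0.8 | 1% | 92% |
| 0.25, 0.75 | 13% | 56% |
| +0.5, −0.5 | 56% | 5% |

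In the shared-shift rows the by-dose test falls below its nominal 5%. The paired differences centre on +s in one order and −s in the other, so their variance is about 1 + s² rather than 1. The larger the shared shift, the more reassuring the test looks.

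In the fourth row, the 56% is detection of the mean shift, (0.25 + 0.75)/2 = 0.5 SD. The part that biases the dose contrast is (0.25 − 0.75)/2 = −0.25 SD. The test of that part, the difference between orders in visit shift, rejects in about 18%. The like-for-like comparison is therefore 13% versus 18%. In the last row the mean shift is zero, so the by-visit test sees nothing.

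**Step 3: the 200 versus 100 mg contrast.** The algebra of Step 1 also applies to a post-dose reading if the shift lasts through the visit. With true dose effect τ, the unadjusted contrast has mean τ + p(π + L100) − (1 − p)(π + L200).

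- *Shared shift s, equal orders:* bias 0, but the variance is inflated as above. With τ = 0.5 SD, an unadjusted paired comparison (a stand-in for the ANOVA's dose effect) has 47% power at s = 0.5 and 25% at s = 1. With visit in the model, power is 56% in both cases.
- *Shared shift s, unequal orders:* bias (2p − 1)s. At 12:8, p = 0.6 and 2 × 0.6 − 1 = 0.2, so a shift of 0.5 SD leaks 0.10 SD into the contrast. The by-dose baseline test rejects in only about 4% of such trials.
- *Carryover that differs by dose, equal orders:* bias (L100 − L200)/2, that is −0.25 SD for 0.25 and 0.75.

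**Step 4: sensitivity to sample size.** On a second scale, where each single reading has within-person SD 1, a shared shift of 1 SD with equal orders is rejected by the by-dose test in about 2% of trials at 12, 20, 30 and 40 participants. The by-visit comparison rejects in 61%, 85%, 96% and 99%.

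**The case against.** The strongest reply is that the plan never calls the paired t-test a carryover check. It compares the doses at baseline and, with equal orders, estimates (L100 − L200)/2, which is exactly the carryover quantity that biases the dose contrast. A shared shift that it misses is one that also cancels from that contrast if it persists. The by-visit difference is no purer a check, since it cannot separate carryover from habituation or any other period effect. This stands. It rules out swapping the by-dose comparison for a by-visit one, as the +0.5/−0.5 row shows.

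Two further replies also stand. The statistical section breaks off and other text is not available, so a visit term or a carryover analysis may exist outside what can be read. And adjusting for the visit's own baseline is not automatically protective, because that reading may itself be shifted.

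The objection does not answer the missing visit term in the ANOVA sentence, which is complete. Cancellation from the mean does not remove the shift from the error, and it fails when orders are unequal.

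**Conclusion.** The point holds in a limited form. On the visible text, a by-dose baseline test cannot show that the two visits started level, and the dose comparison names no term for a visit shift. If such a shift exists and is shared, the cost is mainly lost precision (47% to 25% power against 56%, for shifts of 0.5 to 1 SD and a dose effect of 0.5 SD). A fifth of the shift would leak into the contrast at 12:8, and any change from the visit-2 baseline would be distorted to the extent that the shift fades during the visit. Carryover that differs by dose biases the contrast by half the difference if it lasts through the visit.

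A reader might infer more: that the plan relies on the t-test as its carryover check, that 24 hours has been shown to be too short, or that a shared shift biases the 200 versus 100 mg result. The documents support none of these. They give the test no such role, they hold no data on carryover, and a persistent shared shift cancels from the contrast when orders are equal. The formulas are exact; every size above rests on an assumed sample size, SD and order split.

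**What to change.** - Add visit (period) and dose order (sequence) to the model for the dose comparison. The visit term removes a shared shift from the error and from the contrast. Neither term removes carryover that differs by dose.
- Keep the baseline comparison between doses, adjusted for visit.
- Add the visit-2 minus visit-1 baseline difference with a 95% CI, overall and by dose order. State that the overall shift cannot separate carryover from a period effect, and that the difference between orders is the part that biases the dose contrast.
- Report the number of participants in each order.
- Report the visit-1-only dose comparison as a sensitivity analysis. It is free of carryover but compares different people, so its power is low.
- Show the main result with and without adjustment for the visit's own baseline.
- Do not choose the model on the result of a carryover test.

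If text beyond the break already covers any of this, pointing to it is enough. The cost is about one degree of freedom (19 to 18 at 20 participants) and a little more analysis, all on readings that the protocol already takes. No change to the doses or to the interval between visits is proposed.

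### The ANOVA is meant to show the product's effect on energy expenditure, but its named contrast is one active dose against another, and the available text describes no placebo or untreated period

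*Combined protocol and SAP*

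**What the plan says.** The Study Design section describes the layout: "This study followed a randomized, double-blinded, crossover design". It continues: "Participants reported to the clinical site on two separate visits". At each visit there is a pre-dose measurement, after which "participants consumed supplement 1 or 2", with repeat measurements at 60, 120 and 180 minutes. On spacing: "Testing sessions consisted of two visits per week with a minimum of 24 hours between visits".

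The Statistical Analysis section names the compared conditions as 100 mg and 200 mg. For the pre-dose readings: "A paired t-test was used to assess any differences between the 100 and 200 mg doses for REE and RER at baseline". For the main analysis, one sentence gives both purpose and method: "To determine the effects of Gyngerlean™ on energy expenditure, a repeated-measures analysis of variance (ANOVA) was used to determine differences between 100mg". The comparison in full is "differences between 100mg and 200mg doses for the 60, 120- and 180-time intervals". The available text stops at "A repeated Dunnett's multiple", so the reference level of that step cannot be seen.

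Study Design does not say which supplement is which dose. That the two doses fill the two visits is an inference from reading the two sections together. No placebo, control or untreated period appears in the available text.

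**The concern.** The aim and the contrast answer different questions. An aim about the effects of a product asks what happens with it compared with what would have happened without it. A contrast of two active doses asks whether one does more than the other.

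Two misreadings follow. A null dose contrast could be taken as showing that the product does nothing, although it is equally what two equally effective doses would produce. A rise or fall from the pre-dose reading could be taken as the product's effect, although a change over three hours of resting, fasting and repeated testing could produce or hide it. A larger sample cures neither, because the missing piece is a reference condition and not precision.

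**Working it through.** The documents give no sample size, SD, effect size, alpha or order split, so there is no stated figure to reproduce. Steps 1–4 need none of these.

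**Inputs.** From Study Design: 2 visits, 3 post-dose times, one pre-dose reading per visit, minimum spacing of 24 hours. From Statistical Analysis: doses of 100 mg and 200 mg. Assumed: two sequences (100 then 200, and 200 then 100), as a two-period, two-treatment crossover implies.

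**1. What the contrast estimates.** Let m(t) be the mean at time t without product, and e100(t), e200(t) the dose effects. Then

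[m(t) + e200(t)] − [m(t) + e100(t)] = e200(t) − e100(t).

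The no-product mean cancels. If e100 = e200, the expected contrast is 0, whether both are zero or both are large. If the contrast is truly non-zero, e100 and e200 cannot both be zero, so at least one dose has an effect. The size of either is still unknown.

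**2. Whether changes from baseline supply the missing size.** At each time there are four cell means of change from baseline. Let s be the session-time change, p the visit-2 shift and q the sequence difference:

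- 100 then 200, visit 1: e100 + s
- 100 then 200, visit 2: e200 + s + p
- 200 then 100, visit 1: e200 + s + q
- 200 then 100, visit 2: e100 + s + p + q

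That is 4 means, 5 unknowns and rank 4 at each time; over three times, 12 means, 15 unknowns and rank 12. Adding k to s and subtracting k from both dose effects leaves every mean unchanged. So 0 of 6 per-dose effects are estimable, while 3 of 3 dose differences are. Each 1 point of session-time change moves every within-dose change by 1 point.

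**3. Carryover as a condition on the dose difference.** Let c100 and c200 be carryover into visit 2, defined on the change-from-baseline scale. There are now 21 unknowns, and the rank is still 12. Within-person differences (200 minus 100) average d + p + c100 in one sequence and d − p − c200 in the other, where d = e200 − e100. Their mean is

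d + (c100 − c200)/2.

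With d = 0 and p = 1, (c100, c200) = (0, 1) gives −0.5, (1, 0) gives +0.5 and (1, 1) gives 0. Equal carryover cancels. So does carryover that raises the visit-2 baseline and later readings by the same amount, because it does not enter the change.

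**4. Period as a condition.** With no period term, the pooled paired difference carries bias (2f − 1) × p, where f is the share taking 100 mg first. Per point of p this is 0 at 50:50, 0.1 at 55:45, 0.2 at 60:40 and 0.4 at 70:30.

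**5. Cost of a period term (n assumed).** The error degrees of freedom fall from n − 1 to n − 2. The 95% t multiplier goes from 2.262 to 2.306 at n = 10 (+1.9%), 2.093 to 2.101 at n = 20 (+0.4%) and 2.0452 to 2.0484 at n = 30 (+0.2%). With residual SD σ held fixed, the variance goes from σ²/n to σ²/[4n f(1 − f)]. The standard error is therefore multiplied by 1/√(4f(1 − f)): 1 at 50:50, 1/√0.96 = 1.021 at 60:40 and 1/√0.84 = 1.091 at 70:30. Combined interval widening:

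| Order split | n = 30 | n = 10 |
|---|---|---|
| 50:50 | 0.2% | 1.9% |
| 60:40 | 2.2% | 4.0% |
| 70:30 | 9.3% | 11.2% |

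**The case against.** The best defence is that the ANOVA sentence discloses its contrast openly, so the fault is a broad opening phrase. Each visit has a pre-dose reading, and the incomplete Dunnett step may well compare later times with it. No conclusion about efficacy is visible, and a limitation statement may stand in text that is not available.

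Part of this stands. A reader might infer that the trial, as described, can say nothing about whether the product works. That goes too far: under equal carryover and a balanced or modelled period, a non-zero dose difference is qualitative evidence that at least one dose has an effect. A reader might also infer that the trial had no placebo at all, or that the Dunnett step is at fault. The documents do not support either, because text is missing before Study Design and after the start of the Dunnett sentence.

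Carryover and period bias are secondary. The text allows visits 24 hours apart and names no period term in what can be read, but nothing shows that carryover or an unbalanced order occurred. They are conditions on the dose comparison and do not make the mismatch of aim and contrast any worse.

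The appeal to the pre-dose reading does not succeed. It is one untreated time point, not an untreated period followed for 180 minutes. A Dunnett comparison with it would test product effect plus session time.

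**Conclusion.** The point holds. As described, the named contrast cannot size the effect of either dose, and a null result cannot be read as no effect. Within-dose changes from baseline cannot by themselves be attributed to the product. The dose difference is estimable at all three times, subject to equal carryover on the scale analysed and to a visit order that is balanced or modelled.

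This rests on reading the two supplements as the two doses, and on the absence of a placebo or untreated period from the available text. It does not depend on sample size, SD or effect size; only the interval costs use an assumed n and order split. It matters because it changes what the trial can conclude, in both directions.

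**What to change.** - Restate the aim as comparing the acute effect of 200 mg with that of 100 mg on energy expenditure.
- Report the within-person dose difference with a 95% CI, from a model with participant and period terms, as the main inferential result. Adding sequence to a model with participant terms does not alter this difference and does not resolve carryover.
- State that the estimate assumes equal carryover from the two doses, given the permitted 24-hour spacing.
- Label within-dose changes from baseline, tested or not, as uncontrolled.
- State that a null dose contrast does not show absence of effect.
- If a placebo or untreated period exists outside the available text, name it and make it the contrast for the present aim.

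No new data are needed: the work is rewording and one re-fit using the visit order. The price is a narrower claim and a wider interval: about 0.2–1.9% at a 50:50 split for an assumed n of 30 down to 10, about 2–4% at 60:40 and about 9–11% at 70:30, with residual SD held fixed. At 50:50 the period term removes no bias and costs almost nothing; its larger costs arise at the uneven splits, where it does remove bias.
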